2.3 Risk/Benefit Assessment

2.3.1 Known Potential Risks

Risks of L9LS: There have been no notable safety signals in the VRC 614 phase 1 trial (the first in human study of this product) to date, which includes 12 weeks of follow-up after initial administration and 8 weeks after CHMI. A similar malaria antibody, CIS43LS, was evaluated as safe and well tolerated in the VRC 612 study. 11 Similarly, no significant safety concerns have arisen in the completed trial of CIS43LS in healthy Malian adults at 6 months after product administration. 16 The study in Mali was done with a dose of 40 mg/kg IV (110 participants), 10 mg/kg IV (110 participants), and placebo (110 participants). As described above (Section 2.2.1.3), an ongoing phase 2 trial in Mali is assessing the safety and efficacy of subcutaneous injection of L9LS against P. falciparum infection in healthy children aged 6-10 years over a 6month malaria season (July-December). In Part A (initiated in March 2022), safety was first assessed at three escalating dose levels in adults (n=18), followed by two escalating dose levels in children aged 6-10 years (n=18). In Part B (initiated in July 2022), 225 children aged 6-10 years were randomly assigned (in a 1:1:1 ratio) to receive 150 mg of L9LS, 300 mg of L9LS, or placebo. Before the second malaria season (starting in June 2023) approximately 90% of pediatriac participants were re-enrolled in a 1-year extension and were re-randomized within their original study arms and received placebo or L9LS at the dose they received in year 1 (150 mg or 300 mg; or 150 mg for children who received placebo in year 1). Both the first and second

subcutaneous injections of L9LS were well tolerated and there have been no serious adverse events.

In Part 1 of this study, safety was assessed at three escalating dose levels in older children 6-10 years (n=36), and also at these same doses in children aged 5-59 months (n=36). From the 72 participants, 54 received L9LS. The subcutaneous injections of L9LS were well tolerated and no serious adverse events were reported.

In a preclinical TCR study, L9LS produced membrane and cytoplasmic binding in infrequent ductal and acinar epithelial cells in the human salivary gland which is of unclear clinical significance. Binding occurred in only 1-5% of cells and was scattered without evidence of clustering. Histopathology findings suggests the human salivary tissues were sourced from surgical excisions with evidence of pre-existing inflammation, which may have contributed to the observed binding. We suspect any effect on the salivary glands from L9LS, if present, would be transient due to the clearance of the passively transferred antibody and the rapid turnover of salivary gland epithelium. To address these findings, the trial will exclude any population at an increased risk for salivary gland dysfunction and will prospectively monitor for signs and symptoms that may be indicative of salivary gland hypofunction. Subject matter experts in salivary gland disorders at the National Institute of Dental and Craniofacial Research who are board-certified by the American Board of Oral and Maxillofacial Pathology have agreed to assist the protocol team by being available for consultation throughout the trial. In addition, L9LS is being evaluated in an ongoing phase 1 study in healthy adult volunteers at the VRC to assess safety, tolerability, PK, and protective efficacy, as described in section 2.2.1. Safety assessment in the phase 1 trial includes prospective monitoring for signs and symptoms that may be indicative of salivary gland hypofunction. Since September 13, 2021, 18 subjects have received L9LS either IV or SC, and there have been no SAEs and no safety pauses. All systemic symptoms were only mild to moderate and self-limited. Mild or moderate solicited systemic AEs were reported by 5 subjects (27.8%). Solicited systemic AEs include mild malaise (5 subjects), mild or moderate headache (4 subjects), mild chills (2 subjects), mild or moderate nausea (2 subjects), and mild joint pain (1 subject). There were also 2 related unsolicited AEs that were reported (lymphadenopathy and elevated serum creatinine), both of which were grade 1. All IV and SC administrations were well tolerated. Of the 13 subjects who received L9LS IV, 4 reported mild pain and 1 reported moderate bruising at the site of administration. Of the 5 subjects who received L9LS SC, 2 reported mild pain, 1 reported mild pruritus and 1 reported mild redness at the site of administration. The protocol and consent will be updated if new information about risks and side effects becomes available from the ongoing phase 1 study.

Risks of MAb Administration: Administration of MAbs may cause immune reactions such as acute anaphylaxis, serum sickness, and the generation of antibodies. However, these reactions are rare and more often associated with MAbs targeted to human proteins or with the use of

mouse MAbs that would have a risk of human anti-mouse antibodies.²⁶ In this regard, because L9LS is targeted to a parasite antigen and is a human MAb, it is expected to have a low risk of such side effects.

Typically, the side effects of MAbs are mild to moderate and may include local reactions at the injection site (including pain, redness, bruising, swelling, pruritis) and systemic reactions such as fever, chills, rigors, nausea, vomiting, pain, headache, myalgia, arthralgia, dizziness, fatigue, shortness of breath, bronchospasm, hypotension, hypertension, pruritus, rash, urticaria, angioedema, diarrhea, tachycardia, or chest pain. Healthcare staff will be appropriately trained and necessary medical equipment will be readily available at the clinic where the study agent is administered. Clinical use of MAbs that are targeted to cytokines or antigens associated with human cells may be associated with an increased risk of infections; ²⁶ however, this is not expected to be a risk for a MAb targeted to a parasite antigen.

Severe reactions, such as anaphylaxis, angioedema, bronchospasm, hypotension, and hypoxia, are infrequent and more often associated with MAbs targeted to human proteins or with non-human MAbs, such as a mouse MAb.²⁶ Most administration-related events occur within the first 24 hours after MAb administration.

Published experience with human MAbs directed against cell surface targets on lymphocytes shows that administration of a MAb may be associated with cytokine release, causing a reaction known as cytokine release syndrome (CRS).²⁷ CRS reactions commonly occur within the first few hours of administration and with the first MAb administration received. This is because the cytokine release is associated with lysis of the cells targeted by the MAb and the burden of target cells is greatest at the time of the first MAb treatment. With licensed therapeutic MAbs, CRS is managed by administering histamine blockers.²⁸ Supportive treatment may also be indicated for some signs and symptoms.

Delayed allergic reactions that include a serum sickness type of reaction characterized by urticaria, fever, lymph node enlargement, and joint pains, typically occur several days after MAb exposure and are more commonly associated with chimeric types of MAbs. ²⁶ In general, and with due consideration of the needs dictated by individual subject symptoms and treating clinician discretion, immediate and delayed reactions to study product will be managed according to the principles of the American Academy of Allergy, Asthma, and Immunology guidelines. ²⁹

Participation in this study may limit a subject's eligibility for future MAb studies.

Risks of Placebo Administration: There are no risks of the placebo (normal saline) other than injection related events such as transient vasovagal-mediated hypotension or local site injection bruising, swelling, or infection, the risk of which will be minimized by using sterile techniques.

Risks of Blood Drawing: Drawing blood by venipuncture or fingerprick/ heel prick may cause pain, bruising, and a feeling of lightheadedness or fainting. Rarely, an infection may develop at the site where blood is taken.

Risks of DP Administration: Before study agent administration, all subjects will be given DP, the second-line antimalarial according to the Kenyan national guidelines, to clear any preexisting Pf blood-stage infection. DP is being selected over AL for logistic reasons, as it is administered only once daily for three days, simplifying the process of observing each administration and therefore improving compliance and ensuring parasite clearance prior to MAb administration. Clearance of preexisting Pf blood-stage infection is necessary to accurately assess the primary endpoint of Pf blood-stage infection as detected by microscopic examination of thick blood smear after administration of L9LS or placebo, since preexisting Pf blood-stage parasites cannot be reliably distinguished from newly transmitted Pf blood-stage parasites.

Although there is some evidence to suggest that exposure to Pf blood-stage infection may interfere with the human immune response to malaria vaccine candidates, clearance of preexisting Pf blood-stage infection is not considered necessary for L9LS efficacy since it directly mediates its protective effect against sporozoites and does not depend on induction of any host immune response. 12

Adverse reactions (ARs) to DP are estimated to occur in 1.8% of patients, according to two studies included in a recent meta-analysis.³⁰ Reactions typically do not require stopping treatment. In postmarketing experience, serious hypersensitivity reactions including anaphylaxis and serious skin reactions (bullous eruption) have been reported. Children receiving this medication should have a weight of at least 5 kilograms. Medication like macrolide antibiotics, quinolones, and certain antihistamines like astemizole will be avoided during the period of giving DP. Very common side effects (≥1 in 10) in children include pyrexia; common side effects (≥1 in 100 to <1 in 10) diarrhea, vomiting, abdominal pain, rashes, irregular heart rate, QT/QTc prolongation, leukopenia/neutropenia. Possible side effects will be communicated to the parent/guardian. Individuals with known sensitivity or contraindications to the antimalarials administered in this study are excluded from participation.

In a recently completed therapeutic efficacy trial assessing AL and DP (ClinicalTrials.gov Identifier: NCT05060198), both drugs were well tolerated (<2% of children vomited the first dose of medication in both arms). Only one severe adverse event was recorded—a participant in

the AL arm hospitalized with severe dehydration due to a diarrheal illness; the child recovered fully. This event was deemed unrelated to the study drug.

A complete list of side effects and contraindications is provided in the product Guide for Healthcare Professionals (insert). 31

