2.2.1.2.1 TCR Study

The TCR assay screened a standard panel of normal human tissues (three donors per tissue) and Sprague Dawley rat tissues (two rats per tissue). Mammalian cells transfected to express CSP were used as a tissue-positive control. Two concentrations of L9LS were tested: 1.15 µg/mL (selected as the concentration which saturated the positive control tissue), and 11.5 µg/mL (10-fold excess). A negative control IgG1κ antibody (GR338422-1, no mammalian target antigen) was tested at the same two concentrations. L9LS exhibited scattered specific membrane binding in 3/3 human salivary gland tissue samples and localized to the epithelial cells lining the ducts and acini. Binding was rare (1-5% of these epithelial cells) at 1.15 µg/mL, and rare to occasional (5-25% of these epithelial cells) at 11.5 µg/mL. The cause of the salivary epithelial cell membrane binding has not been identified. Specific membrane binding to salivary gland tissue was not observed for the negative control antibody. L9LS did not bind to rat salivary epithelium. No specific membrane binding to other human tissues was observed.

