In the ongoing phase 2 trial of L9LS in Mali involving healthy children aged 6-10 years, a prespecified exploratory analysis of the relationship between the weight-based dose of L9LS (mg of L9LS administered per kg of body weight) and protective efficacy suggested that ~12 mg/kg of L9LS corresponds to a protective efficacy against clinical malaria of approximately 75% over six months compared to placebo. In addition, preliminary PK analysis indicates that the average half-life of L9LS in Malian children is ~35 days, compared to ~55 days in Malian adults, and ~65 days in U.S. adults. After receiving 10-20 mg/kg of L9LS, the average number of days required for the serum concentration of L9LS to fall below the lower limit of detection (0.61 μg/mL) was 243 (95% CI 232–254). Therefore, we anticipate that a single dose of L9LS in the range of 10-20 mg/kg will not provide high-level protection (>75%) against malaria over 12 months in healthy Kenyan children 5-59 months of age who are exposed to intense perennial malaria transmission. Therefore, the 1-year extension of the phase 2 Kenya trial will assess the safety and protective efficacy of L9LS at a dose range of 20-40 mg/kg.

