8.4.2 Documenting, Assessing, Recording, and Reporting Events

ALL AEs, including those that may appear to have a non-study cause (see "Causality" below), will be documented (e.g., on the clinical chart/progress notes/clinical laboratory record),

recorded (e.g., in the study-specified CRF/research database), and reported (e.g., cumulatively from the research database, or according to protocol-specified expedited reporting mechanism) to the sponsor from the time informed consent is obtained through the timeframe specified below. At each contact with the subject, information regarding AEs will be elicited by open-ended questioning and examinations.

AEs and SAEs will generally be recorded, assessed, and reported according to the timeframes outlined in Table 4.

Table 4. Standard event recording, assessment, and reporting timeframes.

| Event type | Record, assess, and report through |
|--|---|
| Related SAEs | End of subject participation in study, or if study personnel become aware thereafter |
| Unrelated SAEs | End of subject participation in study |
| Non-serious AEs of grade 3 or higher, irrespective of relatedness | End of subject participation in study |
| All malaria episodes, whether related or not, including asymptomatic parasitemias, irrespective of seriousness or severity | End of subject participation in study |
| Related non-serious AEs of grade 1 and 2 | End of subject participation in study |
| Unrelated non-serious AEs of grade 1 and 2 | End of subject participation in study in part 1 and part 1b; 28 days following IP dosing in part 2 and part 2 extension |

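### The promised salivary gland monitoring has no assessment of its own after dosing, and in part 2 and the extension a late, mild salivary event judged unrelated is not recorded

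*Combined protocol and SAP*

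**What the plan says.** Section 2.3.1 (Known Potential Risks) treats salivary gland binding as a finding of unclear clinical significance. It answers it in three ways: excluding children at raised risk, having salivary experts available for consultation, and a commitment that the trial "will prospectively monitor for signs and symptoms that may be indicative of salivary gland hypofunction". It summarises the laboratory result as "Binding occurred in only 1-5% of cells and was scattered without evidence of clustering".

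Section 2.2.1.2.1 (TCR Study) gives the result by concentration: "Binding was rare (1-5% of these epithelial cells) at 1.15" µg/mL, and "rare to occasional (5-25% of these epithelial cells) at 11.5 µg/mL". It found no specific membrane binding in other human tissues and none in rat salivary epithelium.

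On collection of adverse events, section 8.4.2 says that at each contact "information regarding AEs will be elicited by open-ended questioning and examinations". Table 4 in that section sets how long each type of event is recorded. For unrelated, non-serious grade 1–2 events the limit is "28 days following IP dosing in part 2 and part 2 extension". In parts 1 and 1b the same events are recorded to the end of participation.

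On exposure, section 4.2.2 reports from the Mali trial in children aged 6–10 years a half-life of about 35 days. After 10–20 mg/kg, the mean time to fall below 0.61 µg/mL was 243 days (95% CI 232 to 254). Section 1.1 remarks that younger children appear to clear the product faster.

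**The concern.** The salivary gland is the only human tissue in which the cross-reactivity study found specific membrane binding, and it is the one organ for which the protocol promises dedicated follow-up. A reader looking for how the promise is kept finds the relevant signs (dry mouth, swelling under the tongue or below the ear, halitosis) only in exclusion criterion 13, which is applied before dosing.

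The extension moves to 20–40 mg/kg, gives up to two further L9LS doses, and has safety as its first primary objective. If nobody is asked about salivary signs in a uniform way, an absence of reports at the end of year 2 is hard to interpret: it could mean no effect, or that mild effects were not raised, or that they were raised late and classed as unrelated. The rat toxicity study cannot fill the gap, because rat salivary epithelium did not bind L9LS. Section 2.3.1 mentions salivary monitoring in the phase 1 trial but reports no salivary-specific result from it.

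**Working it through.** **Step 1. Is there a salivary item after dosing?** I looked in every place where one could sit.

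| Place | Content | Salivary item |
|---|---|---|
| Schedules 1.4.1–1.4.4 | Examination, vital signs, history, CBC, ALT, creatinine, smear, PK, ADA | None |
| Solicited lists (footnote 5 of each schedule; 6.1.2.4) | Injection-site signs; fever, tiredness, aches, headache, chills, nausea, joint pain | None |
| 8.2.1 | After screening, examination targeted to signs, symptoms and history | None |
| 8.3 | Physical examination, vital signs, CBC, ALT, creatinine | None |
| 8.4.2 | Open-ended questioning and examinations | None |
| 4.1 | Questionnaires on symptoms and care-seeking, including contacts between monthly visits | Content not given |
| Appendix B | Laboratory values and fever | None |
| 5.2, criterion 13 | Salivary signs listed | Yes, for eligibility only |

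**Step 2. What does the analysis compare?** The primary safety endpoint is local and systemic events within 7 days plus serious events throughout. Section 9.5.5 compares arms in the efficacy study on solicited events, related events and serious events. A mild salivary event that is unsolicited and judged unrelated falls outside those comparisons even when recorded; it would appear only in the listings and overall summaries.

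**Step 3. What does the 28-day limit cover?** From Table 4, for part 2 and the extension:

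- Serious events, related or not: to end of participation (related ones also afterwards).
- Grade 3 or higher, related or not: to end of participation.
- Related grade 1–2: to end of participation.
- Malaria episodes, whatever their severity or relatedness: to end of participation.
- Unrelated, non-serious grade 1–2: 28 days after dosing.

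With two dosing visits per year, the last category is recorded for 2 × 28 = 56 of 364 days, or 15.4%.

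**Step 4. How long does exposure last?** The reported mean of 243 days is enough for the point. One window is 28/243 = 11.5% of that period (11.0% to 12.1% over the CI). With first-order decay and a 35-day half-life, the fraction left is 0.5^(t/35): 0.5^(28/35) = 57% at day 28 and 0.5^(84/35) = 19% at day 84.

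**Step 5. The binding figure.** The 1–5% in section 2.3.1 reproduces the result in section 2.2.1.2.1 at 1.15 µg/mL. It does not cover the result at 11.5 µg/mL, whose upper end is 25% rather than 5%.

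**Step 6. Illustration only.** Assume a single-exponential decline through 0.61 µg/mL at day 243, with a 35-day half-life:

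- Level at day 28: 0.61 × 2^((243 − 28)/35) = 43 µg/mL (35 to 54 over the CI).
- Day the level reaches 11.5 µg/mL: 243 − 35 × log2(11.5/0.61) = 95 (84 to 106).
- Day the level reaches 1.15 µg/mL: 243 − 35 × log2(1.15/0.61) = 211 (200 to 222).
- Doubling the dose adds one half-life: limit of detection at about 243 + 35 = 278 days.
- With an assumed 25-day half-life and the same starting level (75 µg/mL): 25 × log2(75/11.5) = 68 days and 25 × log2(75/1.15) = 151 days.

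The documents give no concentration–time data, and the protocol itself plans a two-compartment model. Serum levels also cannot be equated with concentrations applied to tissue sections. These durations show only that the higher tested concentration is not obviously remote from exposure in the first months.

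**The case against.** The best defence is that the protocol is not blind to salivary events. Adverse events are sought at every contact, history and examination are scheduled at every clinic visit, symptom questionnaires are given twice a month, salivary experts can be consulted, and the DSMB meets twice a year. A mild event remains recordable throughout if it is at least possibly related. Section 8.4.2.1.2 sets that bar at a reasonable temporal relationship with little evidence for a likelier cause, and the sponsor reviews causality. An investigator who knows section 2.3.1 may well call a late dry mouth possibly related. The 5–25% result is disclosed in the same protocol.

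Most of this stands, and it rules out three stronger readings that a reader might infer.

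- That mild events in general stop being recorded at 28 days. Table 4 applies the limit only to unrelated, non-serious grade 1–2 events, and only in part 2 and the extension; part 1b, with the 30 and 40 mg/kg groups, records all grades to the end.
- That the 1–5% figure is false. It is the correct result at the lower concentration, and section 2.2.1.2.1 describes the higher one as a 10-fold excess.
- That the trial will yield practically no salivary data. The general routes exist, and the questionnaires and CRFs are not in the documents, so a salivary item in them can be neither confirmed nor excluded.

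The defence does not supply a salivary-specific assessment. General questioning relies on a caregiver volunteering a sign that a child of a few months or years may be unable to describe. After day 28, recording also depends on a judgement of relatedness made event by event.

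**Conclusion.** The point holds in this limited form. The protocol commits to prospective salivary monitoring and specifies no salivary-specific assessment after dosing. In part 2 and the extension, a mild salivary event outside the 56 recorded days is kept only if it surfaces without a prompt and is judged related, while mean detectable exposure after a single 10–20 mg/kg dose is about 243 days. The risk statement gives the result at one of two tested concentrations without naming it.

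The absence of a salivary item and the scope of Table 4 follow directly from the text. The exposure figure rests on Malian children aged 6–10 years and may be too long for younger children here. How often a late salivary event would be called unrelated is unknown, so the loss cannot be expressed as a number of events. No power or type I error is affected. This is a change that should be made, chiefly because the extension raises the dose and has safety as its first primary objective.

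**What to change.** 1. Add the signs in exclusion criterion 13 as a fixed caregiver question and a brief inspection of the mouth and gland areas at the existing clinic visits, through D84 in part 1b and through Y2D364 in the extension. In infants and toddlers the inspection is likely to be the more informative part.
2. Add salivary events to the between-arm comparison in section 9.5.5 or in the detailed analysis plan due before unblinding. With 9 L9LS and 3 placebo children per dose group, part 1b can only list them; the extension, with at most 108 children per arm, can compare them.
3. Add a Table 4 row recording salivary events of any grade to the end of participation regardless of relatedness, as the table already does for malaria episodes.
4. Reconcile section 2.3.1 with section 2.2.1.2.1 by stating both results: 1–5% at 1.15 µg/mL and 5–25% at 11.5 µg/mL. Section 2.3.1 also mentions cytoplasmic binding, which section 2.2.1.2.1 does not report; settle this in the same edit.

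If a CRF or questionnaire already asks about these signs, citing it in section 8.3 covers the first item.

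The cost is one CRF item, one table row and a few sentences, with no new visit, sample or change to dosing or care. The downside is some background reports of dry mouth or halitosis, which the placebo arm will calibrate.
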